Sham feeding is the practice of stimulating gastrointestinal peristalsis without actually ingesting any food into the digestive system (9). Chewing gum is used in postoperative sham feeding to encourage the return of gastrointestinal peristalsis. The physiologic theory that underlies chewing gum with regards to promoting peristalsis and shortening the time to postoperative intestinal recovery includes the idea that oral and masticatory stimulation provided by gum chewing sufficiently simulates food ingestion to stimulate a neurohumoral reflex that increases gastrointestinal fluid secretion. In addition, the vagus nerve, which is involved in promoting peristalsis, may be stimulated by oral stimulation and chewing (10). According to studies, chewing gum reduces the risk of postoperative ileus and shortens the time it takes for the first postoperative flatus and defecation (9–14). By contrast, some studies of patients undergoing surgery have indicated that chewing gum has not been found to significantly reduce average hospital stay days, shorten the onset of the first postoperative flatus and feces, or prevent postoperative nausea, vomiting, or bloating in studies of patients undergoing surgery (10).

Numerous studies have proven that honey has protective properties for the gastrointestinal system. The gut microbiota after honey ingestion showed changes in lactic acid bacteria, which may suggest that honey has a role in regulating gut microbiota (15–17). Honey taken orally guards against gastrointestinal infections such as gastritis, duodenitis, and gastric ulceration brought on by bacteria and rotavirus (18). Oral honey and water administration can reduce the incidence and severity of postoperative nausea and vomiting (19,20). Preoperative intake of honey drink results in significantly less wound infections (21). Literature search could not find any previous study about the postoperative use of honey in stoma reversal or intestinal anastomosis patients. However, studies done in rats showed a statistically significant increase in tensile strength of colon anastomosis, decrease in peritoneal adhesion and improved wound

healing (22–25). Human clinical trials need to be performed to better understand the effect of honey intake following intestinal surgery.

The current practice in stoma reversal and intestinal anastomosis patients in the surgical department of Mayo Hospital Lahore is to allow early water sips, chewing gum and honey intake from the 1st or 2nd postoperative day onwards and to allow full soft oral feeds after the passage of flatus or stool and bowel sounds on auscultation, usually on the 3rd or 4th postoperative day. This practice has yielded apparent improvements in postoperative outcomes, but no research or clinical trials have been performed yet to prove significant differences in results.

Previous literature is deficient in directly comparing chewing gum and honey as effective and cost-effective methods to alleviate or prevent postoperative complications following ileostomy reversal and to improve patient recovery. To fully understand their role in the restoration of intestinal function following surgery, more RCTs are necessary (11).

RATIONALE

The rationale of this study is to investigate and identify interventions that can positively impact the postoperative outcomes of patients undergoing ileostomy reversal. After ileostomy reversal, patients may experience complications such as postoperative ileus, delayed bowel function, or anastomotic leakage. Exploring interventions such as chewing gum and honey could help find simple and cost-effective methods to mitigate these postoperative complications. Previous studies have hinted at the potential benefits of interventions like chewing gum or honey in improving postoperative recovery in various surgical procedures (7,10,29,30,11,14–16,20,26–28).

Previous literature is deficient in exploring the role of honey intake in gastrointestinal surgery and specifically ileostomy reversal, so honey is being investigated in our study to bring novelty and uniqueness to the topic. Although it is a common practice to start early oral intake of honey before starting full feeds in our clinical setup, there is deficiency of literature to prove its efficacy in improving postoperative recovery and reducing complications. This study aims to specifically evaluate the efficacy of honey and chewing gum in the context of ileostomy reversal. Identifying interventions to shorten hospital stays, lower the frequency of complications, or enhance patient recovery may have an impact to maximize the effectiveness and economy of healthcare resources.

OBJECTIVE

To compare the effect of chewing gum and honey on postoperative recovery and complications in ileostomy reversal (as mentioned below).

OPERATIONAL DEFINITIONS

1. **Early enteral nutrition:** Defined as oral intake started on the first postoperative day. In contrast, the traditional way of normal enteral nutrition is nothing by mouth until the resolution of ileus, then a fluid diet, followed by a regular diet (27).

2. **Ileostomy reversal:** When the ileum previously used to form the stoma i.e. Loop Ileostomy, Double Barrel Ileostomy, Ileocolostomy or End Ileostomy is reconnected to the remainder of the bowel internally (31).

3. **Postoperative recovery and complications:**

- **Time to bowel sounds:** Defined as the time, in hours, between the completion of surgical closure and the first audible auscultation of non-continuous, high-pitched bowel sounds originating from the reconnected intestine, documented by a trained healthcare professional using a stethoscope placed over the lower quadrants of the abdomen (32,33).
- **Time to pass flatus:** Defined as the time, in hours, between the completion of surgery and the documented passage of the first objectively confirmed flatus by auscultation or direct observation (33).
- **Time to pass feces:** Defined as the time, in hours, between the completion of surgery and the documented first independent bowel movement, excluding any stool manually evacuated or stimulated by laxatives (33).
- **Time to full feeds:** Defined as the time, in hours, between the surgery and the first point at which the patient tolerates and consumes a regular, unrestricted diet without experiencing any significant postoperative gastrointestinal complications (e.g., nausea, vomiting, abdominal pain, ileus) for a predetermined timeframe (i.e., 24 hours) (7,26).
- **Postoperative pain:** Postoperative pain in stoma reversal surgery was defined as the subjective pain intensity experienced by the patient at rest or during movement, assessed using the Visual Analog Scale (VAS). The VAS consists of a 10 cm horizontal line anchored by "no pain" (score of 0) and "worst imaginable pain" (score of 10), with patients marking the point on the line that best represented their pain intensity (4).
- **Postoperative ileus:** Postoperative ileus is an abnormal pattern of slow or absent gastrointestinal motility in response to surgical procedures. It is measured as the absence of flatus/stool and inability to tolerate an oral diet within 3 days after surgery (34) (35).
- **Postoperative nausea and vomiting (PONV):** PONV is defined as documented postoperative nausea/emesis or administration of a rescue antiemetic (36).
- **Length of postoperative stay:** Defined as the time, in hours, from completion of reversal surgery to the time of discharge from the hospital (14).

HYPOTHESIS

There is a significant difference in the effect of chewing gum and honey on postoperative recovery and complications in ileostomy reversal.

MATERIALS AND METHODS

METHODS

Trial Design: Prospective single-blinded randomized controlled trial. Parallel design with allocation ratio 1:1 will be used. This manuscript is a protocol for the pilot RCT.

Participants: Patients presenting to the outdoor and ward of West Surgical Department with an Ileostomy and undergoing Ileostomy reversal surgery in the operation theatre.

Study Setting and Location: Male and Female Ward, West Surgical Department, Mayo Hospital, Lahore

Sample Size:

Due to deficiency of literature about the use of honey in gastrointestinal surgery and specifically intestinal anastomosis, it was decided that pretesting with a pilot study would be conducted to calculate the sample size. The overall sample size of 30 participants for the pilot trial was selected according to the Rule of Thumb for pilot trial sample size calculation. 15 participants in each group, i.e. Group A for chewing gum and Group B for honey, were allocated randomly using the lottery method. The primary outcome variable was time to pass flatus. The results of the pilot trial for the primary outcome variable showed that the mean time to pass flatus in Group A was 67.73 ± 8.481 hours and Group B was 75.73 ± 9.968 hours.

Outcome Variable	Group A		Group B		Population SD (σ)	Sample Size (n)
	Mean	SD	Mean	SD		
Bowel sounds	51.20	9.937	59.20	8.970	9.466	31
Time to pass flatus	67.73	8.481	75.73	9.968	9.254	29
Time to pass stools	100.80	11.632	119.47	12.994	12.332	10
Time for full feeds	79.47	10.239	93.33	11.178	10.719	13

The means and standard deviations of the pilot trial data was used to calculate the sample size using WHO Sample Size Calculator using the formula for hypothesis tests for two population means (one-sided test) as follows:

$$n = \frac{2\sigma^2(z_{1-\alpha} + z_{1-\beta})^2}{(\mu_1 - \mu_2)^2}$$

Where,

n = Sample size = 60

σ = Population standard deviation = 9.2245

σ^2 = Variance = 85.0914

$Z_{1-\alpha}$ = Confidence level 95% = 1.96

$Z_{1-\beta}$ = Power of test = 95%

μ_1 = Population mean Group A = 67.73

μ_2 = Population mean Group B = 75.73

A total sample size of 60 patients (30 patients in each group) is estimated by using 5% level of significance and 95% power of test with expected mean value time to pass flatus in Group A (Chewing Gum) as was 67.73 ± 8.481 hours and Group B (Honey) as 75.73 ± 9.968 hours in the pilot study.

Sampling Technique: Non-probability purposive sampling. Patients admitted to the hospital for stoma reversal procedure will be assigned into Group A or B using a lottery method, ensuring that the sample population is divided into the two groups equally and randomly regardless of their characteristics (33).

Sample Selection:

Inclusion Criteria:

- All patients of age more than 18 years with an Ileostomy
- Undergoing surgery involving reversal of an Ileostomy i.e., Loop Ileostomy, Double Barrel Ileostomy, Ileocolostomy or End Ileostomy
- Time from fashioning of ileostomy to its reversal is of a duration greater than 1 month

Exclusion Criteria:

- Patients with existing complications as mentioned above in the operative definition of postoperative complications
- Patients with malignancy
- Patients with inflammatory bowel disease
- Patients who cannot communicate well
- Patients who have difficulty chewing or swallowing
- Patients who are prohibited from oral intake by the surgeon
- Patients having undergone Ileostomy reversal more than 1 day before being included in the study

Outcome Measures:

- Primary Outcome
 - Time to pass flatus
- Co-primary Outcomes
 - Time to bowel sounds
 - Time to pass feces
- Secondary Outcomes

- Time to full feeds
- Postoperative pain
- Postoperative nausea and vomiting
- Length of postoperative stay /Time to discharge

Data Collection Procedure:

After the approval to carry out this study from the Research Evaluation Unit (REU) College of Physicians and Surgeons Pakistan and the Institutional Review Board (IRB) King Edward Medical University, subjects meeting the operational definitions and the inclusion & exclusion criteria will be enrolled in the study after informed consent.

Randomization:

Allocation: Patients will be randomly allocated in group A or B: A for the Oral Chewing Gum group and B for the Oral Honey group using the lottery method by the principal investigator.

Sequence Generation: The lottery method is a simple form of simple randomization used to assign participants into the two groups in a way that ensures unbiased allocation. Each participant will be assigned a case number from 1 onwards based on their induction into the study by the principal investigator. 30 identical paper slips will be made and Group A will be written in 15 slips and Group B will be written on the other 15 slips. The slips will be folded to conceal the written text. The slips will be mixed thoroughly and drawn randomly, and the participants will be assigned to a group based on the identifier on the slip, i.e. either Group A (chewing gum) or Group B (honey).

Concealment: The identifier “Group A” or “Group B” will be written on identical slips of paper and the slips will be folded to conceal the written text, ensuring blinding by making them indistinguishable.

Implementation:

The random allocation will be done by the principal investigator. The participants presenting to the out-patient clinic for ileostomy reversal will be admitted to the ward and enrolled into the study after fulfilling the inclusion criteria and passing the exclusion criteria by the principal investigator.

After a period of 24 hours from the ileostomy reversal surgery, the patients will be asked to start early water sips intake according to the ERAS protocol (6). Group A patients will be asked to chew gum for 5 minutes every 4 hours. Group B patients will be asked to eat one half tablespoon of natural honey every 4 hours. The outcome parameters will be assessed and

documented every 8 hours in the case report form by the doctor on duty in the ward. As the data collection schedule will be 8 hourly, the doctor on duty in the ward for each day will be responsible for data collection. The doctors on duty in the ward will be trained by the principal investigator about the data collection procedure. The bowel sounds will be auscultated using a stethoscope placed on the right iliac fossa of the patient's abdomen. The patients will be questioned about whether they have passed flatus and feces and at what time they did so. The patients will be questioned about their last time taking full feeds, nausea, vomiting episodes. A visual analog scale for pain will be used to assess the pain score from 0 to 10 i.e. from no pain to the worst possible pain, subjective to each patient. The postoperative antibiotic, IV fluid, analgesic and PPI regimen will be standardized across the study participants. Relevant investigations to confirm the presence of complications will be carried out. All this information will be recorded in the case report form (attached).

Blinding: Selection bias will be addressed by randomly assigning the participants to the groups. Performance bias could not be eliminated due to different surgeons performing the ileostomy reversal surgery. Detection bias will be addressed by keeping the participants unaware of what group they are assigned to and because of the objective nature of the outcome variables. There will still be some detection bias in some respects involving the subjective opinion of the participants e.g. pain score. Intention-to-treat analysis will be done to address attrition bias.

Follow-up: The primary and secondary outcomes will be assessed at 8 hourly intervals after starting either oral chewing gum or honey 24 hours postoperatively and the data will be written manually in the case report form. The final assessment point will be till the time of discharge or a maximum of 5 days/144 hours postoperatively. Data collection will be concluded when the patients will be discharged by the consultant orders in the ward round. Oral chewing gum or honey intake will be stopped on discharge and the patients will be recommended to continue taking oral meals at home. Further follow-up will be not done after the patients are discharged from the hospital.

Data Analysis Procedure:

Statistical analysis of the data will be carried out using IBM SPSS Statistics V26.0 for the Window program (IBM, Armonk, New York, USA). Qualitative variables such as gender, presence or absence of postoperative complications will be analyzed using frequencies and percentages. Quantitative variables such as age, length of postoperative stay, time to full feeds, time to bowel sounds, time to pass flatus and time to pass feces will be analyzed by calculating their mean and standard deviation. The data collected will be analyzed using descriptive statistics, such as frequencies, percentages, and means. Chi-Square test and logistic regression will be used to analyze the categorical variables whereas continuous variables will be analyzed using student t-test. Outcome data of the three groups will be compared to see the statistically significant difference, p-value of < 0.05 will be considered statistically significant. Outcome data will be stratified for age, gender, operative surgery, postoperative complications and post stratification chi square test will be applied. All qualitative data will be evaluated using

frequency tables. Any changes in the pre-operative and post-operative values will be calculated in absolute as well as percentages. The data will be explored using descriptive studies.

REFERENCES

2. de Gaay Fortman DPE, Kroon HM, Bedrikovetski S, Fitzsimmons TR, Dudi-Venkata NN, Sammour T. A snapshot of intraoperative conditions to predict prolonged postoperative ileus after colorectal surgery. *ANZ J Surg* [Internet]. 2022 Sep;92(9):2199–206. Available from: <http://www.ncbi.nlm.nih.gov/pubmed/35579059>

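### The document calls itself the pilot protocol, reports the pilot as finished, sizes a 60-patient test from it and provides for 30 allocations; it never says whether the pilot patients count toward the 60

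*Combined protocol and SAP*

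**What the plan says.** Four parts of the document bear on this.

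- **Trial Design** describes the document itself: "This manuscript is a protocol for the pilot RCT".
- **Sample Size** gives the pilot's purpose, "pretesting with a pilot study would be conducted to calculate the sample size", and then describes it as done: "15 participants in each group, i.e. Group A for chewing gum and Group B for honey, were allocated randomly using the lottery method". It reports results by arm for four outcomes. For the primary outcome, "the mean time to pass flatus in Group A was 67.73 ± 8.481 hours and Group B was 75.73 ± 9.968 hours".
- **Sample Size**, after the formula, sets the size of the test from those results: "A total sample size of 60 patients (30 patients in each group) is estimated", at 5% significance and 95% power. Data Analysis Procedure plans tests at p < 0.05.
- **Sequence Generation**, in the future tense, provides 30 slips, 15 marked for each group.

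No section says whether the 30 pilot patients are part of the 60 or separate from them.

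**The concern.** A document cannot be the protocol both for a finished pilot and for the powered test sized from that pilot. The slip count adds to the problem. Thirty slips fit a pilot-only protocol, or 30 new patients added to the 30 already treated. They do not fit 60 newly randomised patients unless a second set is drawn, and none is described.

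Two things depend on the answer. The first is what the trial may conclude: a pilot supports planning, whereas a 60-patient test at 5% is meant to be confirmatory. The second is how many new patients supply the evidence. The pilot's flatus result is printed in the protocol and already favours gum. If the treatment of those patients is left open, the decision to include them can be made with half of the combined data known.

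**Working it through.** **Inputs (Sample Size).** Flatus: 67.73 (SD 8.481) for gum and 75.73 (SD 9.968) for honey, 15 per arm; difference 8.00 hours. The table's SD is 9.254; the formula's SD is 9.2245. Significance 5%, power 95%, formula labelled one-sided.

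**1. The plan's own figure.** The two SDs are the pooled value, √((8.481² + 9.968²)/2) = 9.254, and the simple mean, (8.481 + 9.968)/2 = 9.2245. With one-sided z values of 1.645 and 1.645:

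n = 2 × 9.254² × (1.645 + 1.645)² / 8² ≈ 28.96, so 29 per group (28.78, also 29, with SD 9.2245).

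This matches the table's 29, and the text's 30 per group is close to it. The printed z of 1.96 would give 34.8, so 35 per group; that is a separate matter. The 60 therefore comes from the pilot difference.

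**2. Strength of the pilot result.**

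t = 8.00 / (9.254 × √(2/15)) = 8.00 / 3.379 = 2.37 on 28 df; two-sided p = 0.025.

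**3. Chance of significance if the pilot is pooled with 30 new patients and there is no true difference.** With equal halves, Z_pooled = (Z_pilot + Z_new)/√2. Significance for gum requires Z_new > 1.96 × √2 − Z_pilot.

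| Method | Two-sided 5% test |
|---|---|
| Pilot p-value converted to z = 2.24: P(Z > 0.53) | 29.8% |
| Pilot t taken as z = 2.37: P(Z > 0.40) | 34.3% |
| Simulated pooled t-test, 58 df, pilot summaries held fixed, true SD 9.254 | 32.4% |
| Same simulation, true SD 11 to 8 | 27% to 37% |

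On the one-sided basis named for the sample size formula, the two normal approximations give 47% and 52%. If only new patients are tested, the chance is 5%.

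In hours: at SD 9.254 the pooled difference must reach 2.002 × 9.254 × √(2/30) = 4.78. The new patients would then need to favour gum by 2 × 4.78 − 8.00 ≈ 1.6 hours.

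**4. Overall type I error of pooling, not conditional on the pilot.** If the total was fixed at 60 whatever the pilot showed, it is 5.0%. If the total is set from the pilot's observed effect with the one-sided formula and the pilot data are reused, simulation gives 5.4% to 7.3%. The caps used, 30 to 1,000 per group, are an assumption.

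**5. Power from new patients alone, at the pilot effect and SD (t-test).**

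| New patients | Two-sided 5% | One-sided 5% |
|---|---|---|
| 60 (30 per group) | 91% | 95% |
| 30 (15 per group) | 63% | 75% |

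**The case against.** The strongest reply is that pooling is a hypothesis about the plan and that the text leans against it. The pilot's stated purpose was to calculate a sample size. The 60 is justified by expected values taken from the pilot, which treats it as an outside source. Data Collection Procedure enrols in the future tense, after approvals. The exclusion criteria bar anyone whose reversal was more than one day before inclusion, so if the 60-patient trial is a separate study, completed pilot patients would be ineligible. All of this stands, and a reader who infers that the sponsor intends to pool goes beyond the documents. None of it is an explicit exclusion, however, and the 30 slips remain unexplained.

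The second reply concerns the error rate. A reader might infer that the design's false-positive rate is 30% instead of 5%. It is not. A sound fixed 60-patient trial that happened to show this difference at its halfway point would have the same conditional chance and still be a valid 5% test.

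Nor do the documents show that the hypothesis was chosen because the pilot favoured gum: the stated hypothesis has no direction, and flatus is described as the pilot's primary outcome. They also do not give the pilot's site, so it cannot be assumed to be the same.

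**Conclusion.** The inconsistency is established by the text. Trial Design, Sample Size and Sequence Generation cannot all describe the same study, and the status of the 30 pilot patients is unstated. As written, the plan either randomises half its stated number or reaches 60 only by counting patients whose results are known.

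The 30% to 34% figure rests on three conditions: the pilot difference as observed, pooling with 30 new patients, and a two-sided 5% test. It is relevant because the pilot means are already known, but it is not the trial's type I error, which under pooling would be about 5% to 7% depending on how the pilot set the total. Even without pooling, the number of new patients matters: two-sided power at the pilot effect is about 91% with 60 and 63% with 30. This should be settled before the trial's result is read as confirmatory.

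**What to change.** State in Trial Design which study the document covers, and make Sample Size and Sequence Generation agree with it.

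- **Main trial with 60 new patients.** Replace the Trial Design sentence with wording such as: *This is the protocol for the main trial. The completed pilot (15 + 15 patients) was used only for planning. Its patients are not counted in the 60 and are not included in any hypothesis test.* Change the slips to 60, 30 per group.
- **Only 30 new patients.** Analyse them alone, restate the power (about 63% two-sided or 75% one-sided at the pilot effect and SD), and show the pilot separately as descriptive data.
- **Pilot only.** Remove the confirmatory 60-patient claim.

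The cost is protocol wording and, in the first case, a larger set of slips. If pooling was intended, the price is a smaller confirmatory sample with its lower power stated.

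### The sample-size inputs contradict each other on the side of the test; 95% power fits a one-sided test of flatus, but read two-sided 30 per group gives about 91%

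*Combined protocol and SAP*

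**What the plan says.** All the sizing statements are in Materials and Methods, Sample Size. The formula is introduced as one for "hypothesis tests for two population means (one-sided test", and its symbol is z(1-α), not z(1-α/2). The inputs listed under it are "Confidence level 95% = 1.96", "Power of test = 95" (in per cent), an SD of 9.2245 with "Variance = 85.0914", and pilot means for time to flatus of 67.73 and 75.73 hours. The closing sentence gives a total of 60: "30 patients in each group) is estimated by using 5% level of significance and 95% power of test".

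The pilot table above the formula lists per-group sizes of 31 (bowel sounds), 29 (flatus), 10 (stools) and 13 (full feeds). Its SD for flatus is 9.254.

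Three other places bear on the side of the test:

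- The Hypothesis is undirected: "There is a significant difference in the effect of chewing gum and honey".
- Data Analysis Procedure says that "continuous variables will be analyzed using student t-test", with significance at p < 0.05 and no side given.
- Outcome Measures names flatus as primary and lists bowel sounds and feces under "Co-primary Outcomes".

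**The concern.** A one-sided 5% test uses 1.645. The value 1.96 belongs to a two-sided 5% test (or a one-sided 2.5% test). The plan names the first, prints the second and gives a single sample size, so at least one line is wrong. A reader who puts the listed inputs into the printed formula does not get 30 per group.

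Two things are at stake. The first is the stated power: under a two-sided analysis the risk of missing an 8-hour difference in flatus is 9.1%, against 4.8% one-sided. The second is the decision rule. With 58 degrees of freedom the critical t is 1.672 one-sided and 2.002 two-sided. A result between these values could be called significant or not, depending on which part of the plan is cited after the data are seen.

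**Working it through.** **Inputs.** Pilot table: differences of 8.00 h (bowel sounds), 8.00 h (flatus), 119.47 − 100.80 = 18.67 h (stools) and 93.33 − 79.47 = 13.86 h (full feeds); SDs 9.466, 9.254, 12.332 and 10.719. Formula: n per group = 2σ²(zα + zβ)²/δ².

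**Step 1: reproduce the table.** Before rounding up:

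| Outcome | Printed n | 1.645 + 1.645 | 1.96 + 1.645 | 1.96 + 1.282 |
|---|---|---|---|---|
| Bowel sounds | 31 | 30.31 → 31 | 36.4 → 37 | 29.43 → 30 |
| Flatus | 29 | 28.97 → 29 | 34.8 → 35 | 28.13 → 29 |
| Stools | 10 | 9.44 → 10 | 11.3 → 12 | 9.17 → 10 |
| Full feeds | 13 | 12.95 → 13 | 15.5 → 16 | 12.57 → 13 |

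The first pair (one-sided 5%, 95% power) matches all four rows. The second (the printed 1.96 with 95% power) matches none. The third (two-sided 5%, 90% power) matches three and misses bowel sounds.

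**Step 2: use the listed inputs exactly.** 2 × 85.0914 × (1.96 + 1.645)²/8² = 34.56, so 35 per group and 70 in total. With 1.645 in place of 1.96: 2 × 85.0914 × 3.29²/64 = 28.78, so 29. The printed 1.96 therefore was not the value behind 29 or 30.

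**Step 3: power at 30 per group for the planned t-test.** Noncentral t with 58 df and noncentrality δ/(σ√(2/30)). For flatus this is 8/(9.254 × 0.2582) = 3.348; for bowel sounds it is 8/(9.466 × 0.2582) = 3.273.

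| Outcome | One-sided 5% | Two-sided 5% |
|---|---|---|
| Flatus | 95.2% | 90.9% |
| Bowel sounds | 94.4% | 89.6% |
| Stools | above 99.9% | 99.99% |
| Full feeds | above 99.9% | 99.8% |

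Missed-effect risk for flatus: 1 − 0.952 = 4.8% one-sided and 1 − 0.909 = 9.1% two-sided. The normal approximation gives 95.6% and 91.7% power for flatus.

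**Step 4: the two SDs.** 9.2245 is the simple average (8.481 + 9.968)/2. The table's 9.254 is the root mean square √((8.481² + 9.968²)/2), with variance 85.64. The choice does not change n for flatus: 29 one-sided and 35 two-sided at 95% power with either SD.

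**Step 5: uncertainty in the pilot difference.** With 15 per group, 8 ± 2.048 × 9.254 × √(2/15) = 8 ± 6.9, a 95% interval of 1.1 to 14.9 hours.

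**The case against.** The best defence is that the only side the plan states is one-sided. The formula's symbol is z(1-α), all four table entries follow from 1.645, and 30 per group then gives 95.2% for flatus. On that view 1.96 is a stray entry and the 95% is correct. This stands as far as it goes: a reader might infer that the stated power is simply wrong, and the documents do not support that. The two-sided figure rests on an inference from an undirected hypothesis, a t-test with no stated side and the printed 1.96. The inference is reasonable, but it remains an inference.

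A reader might also infer that 95% is reached only for flatus and only one-sided. That is false, because stools and full feeds exceed 99% two-sided.

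On bowel sounds, the table's own one-sided size (31) exceeds the 30 adopted. But the sizing is based on flatus, and the one-sided shortfall is 0.6 points (94.4% against 95%).

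Finally, a four-point correction is small beside the pilot uncertainty: over the interval of 1.1 to 14.9 hours, two-sided power for flatus at 30 per group runs from about 7% to over 99.9%. That is true and limits the weight of the point. It does not reconcile the printed inputs or settle the side of the test.

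**Conclusion.** The contradiction is established from the printed figures alone: a one-sided test, a critical value of 1.96, 95% power and 30 per group cannot hold together. The size of the consequence depends on the side. One-sided at 5%, the stated 95% is right for flatus and marginally missed for bowel sounds. Two-sided at 5%, the more natural reading, power is about 91% for flatus and about 90% for bowel sounds.

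These figures assume that 30 per group are randomised and analysed, and that the pilot differences and SDs are the true values.

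Because the listed inputs give 35 per group, a reader might infer that the trial is too small and should grow to 70. The documents do not support that: power stays near 90% for these two outcomes at the planned size. This is a correction to the specification that should be made, with a modest effect.

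**What to change.** Keep 60 patients, state the side of the test once, and make Sample Size and Data Analysis Procedure agree with it.

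Preferred, two-sided:

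- Data Analysis Procedure: state that the t-test is two-sided at 5%.
- Sample Size, introduction to the formula: delete the one-sided label.
- Sample Size, inputs: print z(1-α/2) = 1.96, use one SD with its matching variance (9.254 and 85.64), and label 60 as the total.
- Replace the 95% power claim with: *30 per group gives about 91% power for time to flatus (8 h, SD 9.254) and about 90% for time to bowel sounds (8 h, SD 9.466), two-sided t-test at 5%, conditional on the pilot difference and SD.*
- Table: recompute the n column by the same method as that sentence. For two-sided 5% and 90% power the t-test needs 31 (bowel sounds), 30 (flatus), 11 (stools) and 14 (full feeds). The 31 is consistent with 89.6% power at 30. Alternatively, label the column as a normal approximation, which gives 30, 29, 10 and 13. Mixing the two methods without a label would create a new mismatch.

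If the sponsor intends a one-sided test: change 1.96 to 1.645, state the direction and justify it on grounds other than the pilot result, state the one-sided test in Data Analysis Procedure, and note 94.4% power for bowel sounds.

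The preferred route costs wording, the table's n column and a lower stated power (95% to about 91% for flatus). It needs no extra patients. Holding 95% two-sided for flatus would take 36 per group (72 in total) by t-test; this is not requested.
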